### **Statistical analysis for primary objective**

Measurements of cancer-core length from transrectal and transperineal biopsies may be compared using a two-tailed, paired samples T test or Wilcoxon Signed Rank Test in order to accept or reject the hypothesis that transperineal biopsy provides higher CCL per positive core than transrectal biopsy.

### **Statistical analysis for secondary objectives**

Cancer detection rate (CDR) and concordance may also be compared between techniques using McNemar's test. Multivariate analysis to determine predictors of improved diagnosis with either technique will be performed using binomial logistic regression.

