#### **4.1 Study participation**

Subject participation includes one standard care biopsy session during which both transperineal and transrectal biopsies will be obtained using ultrasound/MRI fusion guidance to sample suspicious lesions identified on MRI. Two biopsy cores per lesion with MRI suspicion score > 2/5 will be obtained using each approach per standard practice. A follow-up visit after one week will be in accordance with current post-biopsy management practices, and further clinical management will proceed as per standard of care following the biopsy results.

Before enrollment, patients will undergo routine 3 Tesla mpMRI with T2 3D, DCE and DWI imaging following the NYULMC standard prostate imaging protocol. Each study will require approximately 45 minutes to acquire imaging. Prospective candidates for the study will undergo this imaging prior to enrollment into the study and biopsy. The results of the mpMRI will be provided according to the standardized NYULMC template. Lesions identified on mpMRI with high suspicion score (3, 4 or 5 out of 5) will be considered for targeting on biopsy. Men without evidence of lesion on mpMRI or with low suspicion lesions are not eligible for the study.

Study participants will then undergo standard of care pre-biopsy procedure including initiation of peri-procedure antibiotics and pre-procedure Fleets enema. Biopsy will be performed in the Smilow Prostate Cancer Center. All biopsies will be performed using general anesthesia per standard of care protocol. Biopsies will then be performed according to the standard procedure detailed below.

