- c. Concordance of Gleason score between biopsy and prostatectomy- This measurement correlates to the accuracy of the biopsy technique compared to pathological analysis of the excised prostate gland (gold standard) and is the ultimate metric for **characterization of disease**. However, this is likely to include only a small number of study subjects and therefore may not demonstrate a definitive difference between the two techniques.
  - i. *Variable type:* Categorical

- ii. *Potential outcomes:* True concordance, upstage at final pathology, downstage at final pathology
- iii. *Source:* Histological analysis (pathologist's report)

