#### **4.5 Biostatistics**

##### **Sample size justification**

Evaluation of cancer-core length will be the primary endpoint, as reported above. The necessary sample size will be powered to observe a significant difference in CCL between techniques. The limited available data regarding CCL obtained from transperineal targeted biopsy may not serve as an accurate estimate within our population due to potential differences in targeting techniques as well as patient demographics and selection criteria for biopsy.

Our data from a recent study of patients receiving both targeted and systematic transrectal biopsies demonstrated that the mean CCL per positive core per patient is  $4.7 \pm 3.3$ mm in MRI-targeted transrectal biopsies compared to  $2.8 \pm 2.4$ mm in systematic biopsies. The mean difference of 1.9mm was significant ( $p = 0.03$ ) in a cohort of 67 biopsy-naïve men out of 125 recruited at our institution over 9 months, and likely reflected improved sampling of cancer foci. Similarly, retrospective analysis of 601 MRI-targeted transrectal biopsies at our institution demonstrates that the mean difference between the largest CCL

and second largest CCL found on targeted biopsy of the same lesion is  $2.1 \pm 2.4\text{mm}$ . This difference in CCL may also be considered as reflective of a discrepancy in lesion targeting accuracy between two cores. The average of these two estimates of difference in CCL (1.9mm and 2.1mm) is 2.0mm.

For the present study, a conservative estimate of the mean difference in CCL obtained by transperineal vs transrectal targeted biopsy is 1.0mm, or half of the aforementioned difference of 2.0mm. Assuming a tolerance for  $\alpha$  error of 5%, 80% power, and a mean difference of  $1.0 \pm 2.4\text{mm}$ , a sample size of 46 cancer-positive lesions would be needed to demonstrate a difference in targeting ability between the two biopsy techniques.

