Positive results will be compared on a per-lesion basis, where the largest CCL of the two cores taken from each approach will be compared. Preliminary data from MRI-targeted biopsy since 2012 at the NYU SPCC has demonstrated approximately 55% and 95% cancer detection rate among patients with MRI suspicion scores of 4 and 5, respectively. Additionally, the average number of cancer-positive lesions among men with prostate cancer detected on targeted biopsy is 1.2. Given the approximate time-course for the study, accrual rate, cancer detection rate in our previous trial, and potential screen failures, we anticipate that recruitment of 80 patients will be feasible and provide sufficient power to demonstrate a difference of 1.0 mm in cancer-core length between the two techniques. This sample size also accounts for potential screen failure for patients consented who have not yet had their standard of care MRI of the prostate.

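### Gleason concordance is defined with three outcomes and none for a missed cancer, yet is assigned McNemar's test with no rule for turning it into a paired yes/no outcome

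*Combined protocol and SAP*

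**What the plan says.** Section 4.3 Endpoints, outcome variable c, is "Concordance of Gleason score between biopsy and prostatectomy". It is categorical, with these outcomes: "True concordance, upstage at final pathology, downstage at final pathology". (The plan uses stage words for what is a grade comparison; below, 'upgraded' means that the prostatectomy grade is higher than the biopsy grade, so the biopsy undergraded.) The same item says that this measure "is the ultimate metric for" disease characterization, and then concedes that "this is likely to include only a small number of study subjects and therefore may not demonstrate a definitive difference between the two techniques".

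The analysis is one sentence in section 4.5, Statistical analysis for secondary objectives: "Cancer detection rate (CDR) and concordance may also be compared between techniques using McNemar's test".

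The pairing comes from section 4.1: "Two biopsy cores per lesion with MRI suspicion score > 2/5 will be obtained using each approach per standard practice". A unit of comparison is stated only in the core-cancer-length paragraph of the sample size section: "Positive results will be compared on a per-lesion basis, where the largest CCL of the two cores taken from each approach will be compared". No unit is given for concordance. Nor is there a rule for reducing three outcomes to two, or for an approach whose cores were benign.

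**The concern.** McNemar's test compares two paired proportions, so someone must decide what counts as yes. The obvious choice, concordant versus not, treats opposite errors as the same. Undergrading at biopsy is what poor sampling produces, and poor sampling is the failure that section 3.1 describes. Overgrading is a different matter. Two approaches with opposite error patterns could look identical.

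The second gap is the missed cancer. With only two cores per approach in each lesion, one approach can be positive and the other benign. A man can still reach prostatectomy on the strength of the positive approach, or because his cancer was already known (section 4 admits such men). The benign approach has no Gleason score and fits none of the three outcomes. Without a rule, an analyst would probably leave that pair out, which favours whichever approach misses more. With few prostatectomies, recoding a handful of pairs can change the result, and in an open-label study the coding could be chosen after the results are known.

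**Working it through.** **Is there a plan figure to reproduce?** Not for concordance. The only computed figure in the plan is 46 cancer-positive lesions for core cancer length: (2.4 × (1.960 + 0.842) / 1.0)² = 45.2, rounded up to 46. It reproduces, and has no bearing on this point. The documents give no concordance rates and no expected number of prostatectomies, so every count below is an assumption made to show the mechanism.

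**Method.** Exact two-sided McNemar: with b and c discordant pairs, p is the two-sided binomial probability of a split at least as uneven as b versus c among b + c trials at probability 0.5.

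**Step 1, pooling.** Assume 20 prostatectomy cases. Each approach is concordant in 12 and wrong in 8. All transrectal errors are upgrades at prostatectomy and all transperineal errors are downgrades. Suppose both are concordant in 6, only transrectal in 6, only transperineal in 6, and neither in 2 (total 20).
- Concordant yes/no: 6 versus 6, p = 1.00.
- Upgraded yes/no: 8 versus 0, p = 2 × 0.5⁸ = 0.008.

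**Step 2, a milder pooling example.** One approach has 12 concordant, 7 upgraded, 1 downgraded; the other has 12, 2 and 6.
- Pooled errors: 7 + 1 = 8 and 2 + 6 = 8, no difference.
- Undergrading at biopsy: 7/20 = 35% and 2/20 = 10%.
- Exact McNemar on upgraded yes/no depends on how many men are upgraded under both approaches: from 5 versus 0 (p = 0.06) to 7 versus 2 (p = 0.18). The difference in estimates is masked, but it would not be significant at 5% either way.

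**Step 3, missed cancers.** Assume 20 cases. Fourteen are positive by both approaches, with 2 concordant only by transperineal and 2 only by transrectal. Six are missed by transrectal and correctly graded by transperineal.
- Misses dropped: 2 versus 2, p = 1.00.
- Misses counted as not concordant: 2 + 6 = 8 versus 2, p = 0.11.
- With 8 misses in place of 6 (14 + 8 = 22 cases): 10 versus 2, p = 0.039.

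If the grading errors among the 14 are all undergrading, 'undergraded or missed' gives the same splits.

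**Step 4, how many cases could be affected.** If each approach detects a cancer independently with probability s, the share of cancers found by at least one approach but missed by exactly one is 2s(1 − s) / (1 − (1 − s)²). For s = 0.6, 0.7, 0.8 and 0.9 this gives 57%, 46%, 33% and 18%. Both approaches aim at the same planned targets, so detection is likely to be positively correlated, which would lower these shares.

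**Step 5, what small numbers allow.** Five discordant pairs all in one direction give p = 0.063 and six give p = 0.031. At least six are needed for p < 0.05.

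**The case against.** A reader might infer that the plan pools the two errors and excludes missed cancers. The documents do not say so. Section 4.3 has no exclusion rule and section 4.5 has no collapsing rule; a benign approach could equally be coded as upstaged or as non-concordant. What is shown is an unspecified coding, with pooling and loss as the likely default.

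A reader might also infer that McNemar's test cannot be used at all. That goes too far: concordant versus not is an ordinary binary reading. The fault is that the binary outcome is not named and the obvious one ignores direction. The remedy below collapses levels too, placing downgrading with concordance. It differs in being declared in advance, following the direction of the rationale, and coming with the full table.

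The strongest counter-argument is that misses are already counted. The cancer detection rate is a named outcome in 4.3, is the basis for secondary endpoints in 4.4, and has its own McNemar test. Concordance among men positive by both approaches is a legitimate conditional comparison, and coding misses as grading failures brings detection into a grading endpoint. This stands in part: the conditional comparison should be kept and labelled as such. But the detection rate does not repair a concordance comparison from which missed cancers have silently gone.

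The importance is also limited. Concordance is absent from the objectives in 2.1, the analysis is worded as optional, and the plan concedes small numbers. All of this stands.

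**Conclusion.** The mismatch is real: a three-level outcome with no place for a missed cancer is assigned a test that needs a yes/no outcome, with no rule linking the two. Under the natural reading, opposite errors would be pooled and one-sided misses would probably leave the comparison.

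The consequence is confined to a small, non-primary endpoint. The primary analysis, the sample size and the cancer detection comparison are unaffected. No effect size can be stated from the documents. The illustrations rest wholly on assumed counts, and the p = 0.008 contrast needs all errors of one approach to be upgrades and all errors of the other to be downgrades. A reader might conclude that a significant difference is being hidden. The documents cannot support that, and the milder 7 versus 2 example does not reach significance. The change is still worth making, because it costs little and the plan gives this measure such standing as a gauge of characterization.

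**What to change.** In section 4.3:
- Define concordance per man: the highest Gleason score found by each approach against the prostatectomy score. This avoids mapping lesions to the surgical specimen, for which the plan has no rule, and avoids clustering of up to three targeted lesions within a man.
- Add a fourth level: cancer not detected by this approach.

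In section 4.5:
- Compare 'undergraded or missed at biopsy, yes/no' between approaches with an exact McNemar test.
- Report the full paired table, with upgrading, downgrading and misses shown separately.
- Add a sensitivity analysis limited to men positive by both approaches, labelled as conditional on detection.
- Treat any Stuart-Maxwell or Bowker test as supportive only, in exact or permutation form given the small numbers.
- Keep McNemar's test for the cancer detection rate.

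The cost is a few sentences and minor programming. No extra patients or biopsies are needed, and the prostatectomy pathology report is already the stated source. The downsides are that measured concordance will look lower for both approaches, that a miss will contribute to both this endpoint and the detection rate, and that a per-man definition records a miss only when all of an approach's targeted cores in that man are benign.

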## **5. DIAGNOSTIC AGENTS**

### **5.1 Pre-Enrollment Procedures**

#### **A. MRI: Multi-parametric MRI of the Prostate**

Eligible candidates for this study will have undergone a pre-biopsy mpMRI of the prostate as part of their standard care. Men identified as having highly suspicious regions on this MRI will be offered enrollment into the study to target these areas. All mpMRI procedures will have been performed according to standard of care for

this radiology procedure. All mpMRI of the prostate will be performed using a 3 Tesla magnet following the NYULMC standard prostate imaging protocol. Imaging will be conducted by pelvic phased array coils. No endorectal coil will be utilized. Suspicion of cancer will be graded according to the standard NYULMC Department of Radiology scale.

## 5.2 Diagnostic Intervention

B. Artemis Biopsy: Artemis, Eigen's 3-D prostate imaging device, is a FDA approved Class II medical device for planning and guiding a transrectal prostate biopsy.

In MRI/TRUS fusion planning, the previously available imaging study (MRI) is used by a trained radiologist to mark out regions of interest for targeting. This information is transferred to Artemis when a fusion plan is initiated. The MRI image and the 3D TRUS image are co-registered, and regions of interest marked on the MRI are mapped on to the 3D TRUS image. The urologist then plans biopsy targets in these regions of interest that are overlaid on the 3D TRUS image.

After planning, traditional needle guidance to the planned location as per normal biopsy technique is performed. At all times, the physician uses the live ultrasound image and Artemis guidance to biopsy tissue from the planned location. Transrectal Artemis biopsy is not investigational. This is currently the standard of care biopsy in our practice at NYU. It is FDA approved for this application, has several publications regarding technique from many institutions, and NYU urologic oncologists have performed roughly 1200 such biopsies at NYU since 2009, as part of our standard clinical protocol.

A new attachment will be added to the Artemis device to facilitate transperineal targeted biopsy. Transperineal biopsy itself is not investigational. This is a well-described biopsy technique that is used often in contemporary clinical practice, frequently to improve sampling when patients have a history of negative transrectal biopsies. The attachment to the Artemis device does have 510K regulatory clearance and we do not anticipate additional risks to standard of care transperineal biopsy.

After obtaining 2 cores of the suspicious lesion via transrectal Artemis biopsy, the patient is repositioned to allow for transperineal needle access. The Artemis fusion system allows for visualization of the previously accessed target and 2 additional cores are obtained via transperineal placement of the biopsy needle. For sequential patients, we will switch the order (transperineal before transrectal) for every other patient in order to mitigate any bias from starting with the same approach for each case.

## 6. STUDY WORK FLOW

### 6.1 Recruitment

Subjects will initially be identified from the population of men undergoing outpatient management for suspected or known prostate cancer at NYU Smilow Prostate Cancer Center. Potential participants will be those under the care of the investigators. A member of the research team will screen the patients for eligibility for the study through chart review, and all information will be obtained either directly from the patient and/or their medical record. Screening criteria include PSA history, digital rectal exam, and mpMRI to determine initial eligibility, which will be followed by evaluation of exclusion criteria for enrollment into the study. Any information collected for this study in a patient who is determined to be ineligible will be destroyed.

A member of the research team will inform patients of their eligibility for the trial and potential risks and benefits. Decision as to whether or not to take part in this study is completely voluntary and formal consent will be obtained prior to pre-treatment evaluation.

## **6.2 Study Timeline**

- i. Visit 1 (week 0)
  - a. Baseline visit to determine patient eligibility based on careful review of patient medical history and risk for prostate cancer. If available, patient mpMRI will be reviewed as well. This visit will occur as part of their standard clinical care with the investigator for suspected or known prostate cancer. The research team will review the consent form with the potential subject and answer all questions. Once eligibility is confirmed and the patient agrees to participate in the study, informed consent is signed, and the patient will be scheduled for prostate biopsy at their next visit (2-4 weeks).
  - b. If no mpMRI is available, the patient will be scheduled for this imaging study as per our institution's standard of care before finally determining eligibility. This will be done regardless of participation in the study.
- ii. Visit 2 (week 2-4)
  - a. Approximately 2-4 weeks after the initial visit, each subject will return for prostate biopsy. All biopsies will be done in one operative session and will be performed as outpatient procedures.
- iii. Visit 3 (week 4-5)
  - a. All study participants will have a follow up visit approximately one week following biopsy for clinical evaluation of recovery from biopsy and to review biopsy results. At this point, all patients will be managed according to standard of care based upon biopsy results.

## **6.3 Evaluation During and After Intervention**

Subjects will be monitored by a qualified anesthesiologist during and after the procedure. Following the biopsy, patients will be relocated to the recovery bay adjacent to the procedure room for observation. All patients will be evaluated clinically one week after

biopsy to assess for biopsy complications including risk of infection, persistent hematuria or rectal bleeding. Any identified complications will be recorded and treated according to severity.

## **7. TOXICITY / SIDE EFFECTS (Adverse Event Reporting)**

### **7.0 Definitions:**

- 7.0.1** Adverse Event: Any unfavorable and unintended sign, symptom or disease temporally associated with the use of a medical treatment, regardless of whether it is related to the medical treatment.
- 7.0.2** A serious adverse event (SAE) is defined as any adverse event that results in death, a life-threatening experience, inpatient hospitalization, prolongation of existing hospitalization, persistent disability, or congenital anomaly or birth defect.
- 7.0.3** Study therapy is the required treatment or procedure defined on the protocol.
- 7.0.4** Non-protocol therapy is defined as any treatment or procedure not described in the protocol

### **7.1 Adverse event assessment:**

- 7.11** The type of event using NCI Common Toxicity Criteria for Adverse Events (CTCAE) version 3.0 will be identified and graded for severity.
- 7.12** The relationship of the adverse event to the therapy or procedure will be determined as follows: Unrelated; Unlikely; Possible; Probable; Definite
- 7.13** For reporting purposes, an adverse event is considered unexpected when either the type of event or severity of the event is not listed in the study consent

### **7.2 Serious Adverse Events (SAEs):**

- 7.11.A** All study-related, unexpected Grade 3 or 4 SAEs will be immediately reported to the IRB. These toxicities will be reviewed by the principal investigator and appropriate measures taken in terms of delaying, modifying or stopping therapy.
- 7.11.B** The descriptions and grading scales found in the revised NCI Common Terminology Criteria for Adverse Events (CTCAE) version 3.0 will be utilized for adverse event reporting (<http://ctep.cancer.gov/reporting/ctc.html>).
- 7.11.C** SAEs must be followed until resolution or deemed irreversible.

### **7.2 Routine reporting:**

- 7.21.A** Institutional Review Board rules.  
A reportable events log will be kept over the course of the study for all adverse events as well as all protocol deviations and exceptions. This log will be submitted to the IRB for review during each annual continuation submission.

### **7.3 Potential Adverse Events**

This is a minimal risk study where loss of confidentiality is a potential risk. The PI will adhere to a data monitoring plan to ensure there is no breach in confidentiality.

-There is also risk associated with prostate biopsy (transrectal or transperineal). This includes bleeding, infection, urinary retention, and erectile dysfunction. Because it is not standard to have both approaches done in one sitting for a biopsy, the PI will also monitor the study for an unexpected increase in risk for these potential adverse events.

### **7.5 Potential Benefits of Study**

- This study provides an additional opportunity to sample areas of suspicion for prostate cancer, and may help better characterize disease to provide more information to guide subjects' treatment. It is hoped the knowledge gained will be of benefit to others in the future

